Statistical Analysis Plan

Project Title: Cyclical Neuroactive Steroid Changes, Arousal, and Proximal Suicide Risk: An Experimental Approach

Principal Investigator: [name]

Approved as of September 24, 2019

Statistical Analysis Plan

There are twelve total outcomes, which are specified and numbered (#) below. In order to better set up the power analysis details that follow, I have noted the anticipated intra-class correlations for each outcome (in red) and note from which preliminary data these estimates arise.

OUTCOME SPECIFICATION

- Suicide Outcome Variables. In our primary analyses, proximal suicide risk will be operationalized as (1) daily severity of suicidal ideation using the total score on the Adult Suicidal Ideation Questionnaire in the daily survey (ICC=.64 in K99 trial), (2) daily suicidal planning thoughts (dichotomous) on the daily C-SSRS phone risk screen (~10% of days were positive for planning in the K99 trial; ICC=.45 in K99 trial) and (3) daily suicide attempt (dichotomous; aborted, interrupted, or full) on the daily C-SSRS phone risk screen (~1.2% of days were positive for suicide attempt in the K99 trial; ICC=.12 in K99 trial).

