For each outcome, we will use model fit indices to select the best-fitting hierarchical model before proceeding with analyses. Based on our prior study (K99MH109667) with an similar experimental design and similar data collection structure for daily surveys and lab visits, we expect that the data structure for primary analyses will be observations nested within participants (two-level regression model). In our prior models, inclusion of a third level of nesting (i.e., observations nested within condition nested within individuals) did not improve model fit and did not substantively alter hypothesis tests. Based on the prior study, we also expect that a combination of a random intercept for participant and an autoregressive (day-1) within-person error structure will be included based on model fit.

Testing Experimental Effects: Both of our two aims require that we first evaluate the impact of the experiment on each of the 3 primary suicide outcomes and 9 (RDoC, neurosteroid) mediators described above. Therefore, we will first examine effects of the within-person hormone stabilization experiment on repeated measures outcomes across the menstrual cycle.

- a. For daily outcomes, we will utilize multilevel models (with 52 days—26 per condition-nested within each individual; two-level models) to predict each repeated measures outcome from covariates (daily pain, illness, PRN medication use) and the interaction between (1) experimental condition (a dichotomous variable coded as 0 for natural hormone withdrawal condition and 1 for hormone stabilization condition) and (2) condition phase, a categorical (contrast) variable coded as follows: *midluteal baseline phase*, coded as days +1 to +7 after the positive ovulation test, *perimenstrual experimental phase*, coded as days +11 to +17 after the positive ovulation test, and the *medication withdrawal phase*, coded as days +22 to +26 after positive ovulation test (see Figure 6 in grant for study design and timeline). Number of daily observations per person. For the primary contrast between the midluteal and perimenstrual experimental phases, there are 28 observations per person—14 per condition (7 midluteal, 7 perimenstrual). Based on our preliminary data from the K99 trial (identical experimental manipulation), we anticipate receiving an average of 24 observations per participant.

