3. Testing Interactive Effects of Hopelessness and Arousal on Suicide Outcomes: Interactions among hopelessness and arousal will be examined as predictors of suicide outcomes and as mediators of the experimental effect. In order to test this, we examine day-to-day interactive effects of daily person-centered hopelessness (noted above) and daily person-centered arousal indices (noted above) predicting same-daily suicide outcomes (noted above). We predict that higher-than-usual hopelessness on a given day will predict greater same-day risk on suicide outcomes, but only when arousal is *also* higher than usual for that individual.

4. Evaluating Mediation Where Appropriate. Finally, each aim indicates that **mediation** will be explored as appropriate. Only when analyses indicate significant effects of the experiment on both the suicide outcome and any mediator, as well as significant associations between the person-centered variable (or interaction variable) and the suicide outcome, we will utilize methods provided by **Bauer**, **Preacher**, **and Gil (2006)** to construct a confidence interval for the level 1 indirect effect of experimental condition (condition X phase) on the suicide outcome via the mediator.

1 R01 MH120843-01 (PI: [name]) POWER ANALYSIS.

With the funds allowed in this four-year grant, we are able to increase our proposed sample size slightly, from 80 to 85 completers, which would allow us to achieve 80% power to detect conventionally small-to-medium sized effects that, in our estimation, are clinically meaningful (i.e., $f^2 = .10$, which would mean that the interaction of condition and phase had uniquely accounted for 10% of the variance in the outcome in the perimenstrual window; Selya et al., 2012, "A Practical Guide to Calculating Cohen's f², a Measure of Local Effect Size"). We posit that if hormone withdrawal (vs. experimental stabilization) does not account for at least 10% of the variance in the outcome during this critical risky window of the menstrual cycle, then this line of research, which involves significant participant burden, is not worth pursuing further.

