- Power in multi-level models has a unique consideration beyond sample size and alpha; it is dependent also on the intraclass correlation (ICC) and its implications for the independence of level-1 observations (i.e., the design effect). High ICCs indicate little variation of the outcome within a given person (i.e., stability of repeated observations within a given person), and suggest that the study's power depends more on the number of higher-level units. Low ICCs indicate high within-person variation within a given person and suggest that the study's power depends more on the number of lower-level units. As the ICC ranges from 0 to 1, the effective n will range from the number of lower-level units to the number of higher-level units. In general, the lower the ICC, the higher the power.
- Snijders and Bosker (1999; *Multilevel Analysis: An Introduction to Basic and Advanced Multilevel Modeling*) provide equations to determine the "Design Effect", which we have used to calculate the "effective lower-level N" based on our expected ICCs for each outcome and our expected number of raw observations with 85 completer participants (including 15% missing at daily level and an average of .25 missing visits per person). Once the design effect and effective N is calculated for a given outcome, one can calculate power to detect a given effect size (in our case, f² = .10) for a given number of these *effective* lower-level units (observations or visits)— see Table below for estimates for the current design. We considered a single fixed regression coefficient in a model with 3 predictors, one-tailed test, alpha=.004.
 

Variable	Measureme nt interval	ICC	Upper-Level Sample Size	Effective Lower- Level N based on ICC and Design Effect Equation	Power Achieved to detect f ² = .10
Suicidal Ideation	Daily	.64	85	130	.81
Suicidal Planning	Daily	.45	85	180	.93
Suicide Attempt	Daily	.12	85	542	.99
Beck Hopelessness Scale	Daily	.32	85	244	.98
Brief Agitation Measure	Daily	.26	85	292	.99
Accelerometer activity	Daily	.54	85	152	.88
Typing Speed Instability	Daily	.38	85	209	.96
HRV withdrawal in the lab	Labs	.50	85	163	.90
PEP shortening in the lab	Labs	.50	85	134	.83
Allopregnanolone in serum	Labs	.29	85	177	.93
PBMC gene expression for 3a- HSD	Labs	.50	85	134	.83
PBMC gene expression for 5a- reductase	Labs	.50	85	134	.83

1 R01 MH120843-01 (PI: [name])

Additional Requested Supplemental Table (2019-08-16)

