Variable	Measurement interval	ICC in pilot data	P value	f-squared	Participants Needed to Achieve 80% Power in Proposed Model*
Suicidal Ideation	Daily	.64	.004	.10	83
Suicidal Planning	Daily	.45	.004	.10	57
Suicide Attempt	Daily	.12	.004	.10	21
Beck Hopelessness Scale	Daily	.32	.004	.10	45
Brief Agitation Measure	Daily	.26	.004	.10	37
Accelerometer activity	Daily	.54	.004	.10	71
Typing Speed Instability	Daily	.38	.004	.10	52
HRV withdrawal in the lab	Labs	.50	.004	.10	74
PEP shortening in the lab	Labs	.50	.004	.10	74
Allopregnanolone in serum	Labs	.29	.004	.10	53
PBMC gene expression for 3a-HSD	Labs	.50	.004	.10	74
PBMC gene expression for 5a-reductase	Labs	.50	.004	.10	74

[figure not shown]
*First, we calculated the number of observations required using a normal GLM framework (non-multilevel). Then, we calculated how many participants would be required to achieve that number of adjusted observations after penalizing for the anticipated design effect, which adjusts for the degree of non-independence in values (Snijders & Bosker, 1999) using the anticipated intraclass correlation (ICC) for each outcome. Anticipated ICCs are based on pilot data from prior studies.

1 R01 MH120843-01 (PI: [name])

• Plotting Power Across a Range of Participant-Level Sample Sizes. In addition, one can use the design effect equation to calculate expected power for a range of upper-level sample sizes (i.e., number of participants) adjusting for the most stringent design effect at that repeated measures interval (based on ICC=.64 for daily variables); see the figures below for power estimates across a range of possible participant-level sample sizes.

Effect of Number of Completer Participants on Power to Detect Effects of Intervention on Daily Outcomes in a Two-Level Regression Model (Days Nested within Participants)

[figure not shown]
(Inputs: Fixed Regression Model, 3 predictors, Bonferroni-corrected alpha=.004, Corrected for Design Effect Based on largest expected ICC of .64, and assuming 15% missingness per person)

Number of Completer Participants (Level-2 Units)

Effect of Number of Completer Participants on Power to Detect Effects of Intervention on Laboratory Outcomes in a Two-Level Regression Model (Visits Nested within Participants)

(Inputs: Fixed Regression Model, 3 predictors, Bonferroni-corrected alpha=.004, Corrected for "Design Effect" Based on largest expected ICC for lab visits .50, and assuming an average of .25 missing visits per person)

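### The SAP's power tables apply a between-person design effect to a within-person crossover contrast, so the stated effective Ns, powers and required Ns do not describe this design

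*SAP*

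**What the plan says.** The effect to be tested is set out in the SAP under Analytic Steps. It is the interaction of condition with condition phase. Each participant goes through both conditions, and each condition supplies seven midluteal and seven perimenstrual days. That makes 28 days per person, of which "we anticipate receiving an average of 24 observations per participant". The expected model, subject to fit, has a random participant intercept and first-order autoregressive errors within person. No random slope is named.

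Under Power Analysis the completer sample goes "from 80 to 85 completers", "which would allow us to achieve 80% power to detect conventionally small-to-medium sized effects". The target is f²=.10, explained as the interaction having "uniquely accounted for 10% of the variance in the outcome in the perimenstrual window". The method is a design effect driven by the ICC, followed by an ordinary regression calculation: "We considered a single fixed regression coefficient in a model with 3 predictors, one-tailed test, alpha=.004". The stated direction is "In general, the lower the ICC, the higher the power".

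The footnote to the supplemental table confirms the method for the required Ns: "Then, we calculated how many participants would be required to achieve that number of adjusted observations after penalizing for the anticipated design effect". Suicidal ideation ("ICC=.64 in K99 trial") has the largest requirement, 83 participants, and its ICC fixes the daily power curve.

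**The concern.** The divisor 1+(m−1)ICC is the variance inflation for a predictor that takes one value per person, such as a parallel-group treatment. Condition by phase is not such a predictor, because every completer fills all four cells. What a participant carries through all her observations subtracts out of the contrast, so the between-person variance that the ICC measures cannot inflate its standard error.

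If so, the stated powers (.81 to .99) and required Ns (21 to 83) answer a question about a different design. The quantities that do govern precision here are the residual variance, the autocorrelation and any person-to-person variation in the condition-by-phase effect. None of them enters the calculation.

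There is a practical consequence too. Protocol section 2.0 reports the prior trial's effect on ideation as about one person-standard-deviation. If that is taken as one within-person SD, f² is 1/16 = .0625. The SAP's method gives this effect only about .56 power at 85 completers. A reader of the tables could therefore think a replication of the sponsor's own result is beyond reach.

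**Working it through.** **Inputs from the SAP.** 85 completers; 24 daily observations per person, hence 6 per cell; 3.75 lab observations in the primary contrast (4 less .25 missing); ICC .64 (ideation), .26 (agitation) and .50 (most lab outcomes); f²=.10; one-sided alpha .004; 3 predictors.

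**Reproducing the SAP.** Effective N = 85m/[1+(m−1)ICC], with power from a noncentral t with noncentrality √(f²N) and N−4 degrees of freedom.

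- Ideation: 85×24/(1+23×.64) = 2,040/15.72 = 129.8, power .816 (SAP: 130, .81).
- Lab, ICC .50: 85×3.75/(1+2.75×.50) = 318.75/2.375 = 134.2, power .832 (SAP: 134, .83).
- Required N: 126 observations give 80% power, and 126×15.72/24 = 82.5 (SAP: 83).

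Eleven of the twelve effective Ns match, and all twelve powers match within two points when the stated effective N is used. The HRV row (163) does not fit the lab count. It equals 85×24/12.5, the daily count at ICC .50. The method is not in doubt.

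**Variance of the actual contrast.** Let σ be the residual SD within person and τ the SD between persons of the condition-by-phase effect. With 6 independent days in each of four cells, the variance of the estimated contrast is [τ² + 4σ²/6]/n. The random intercept does not appear. With four equal cells, a contrast δ explains δ²/16 of variance.

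- Residual scale: f²=.10 gives δ = √1.6 = 1.26σ, and effective N = 16×85/(4/6) = 2,040. The ICC drops out.
- Total scale: σ² is .36 of total variance for ideation, so δ = 1.26/√.36 = 2.11σ, and effective N = 2,040/.36 = 5,667. Effective N rises with the ICC.

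To see the direction with power below 1, take a total-scale f² of .005. Simulated power with 85 participants rises from .74 at ICC .12 to .99 at ICC .64. The SAP's table runs from .99 down to .81.

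**Adding the planned AR(1) errors.** The documents give no autocorrelation, so ρ is assumed. Generalised least squares with 6 consecutive days per cell replaces 4/6 = .667 by .923 (ρ=.2) or 1.714 (ρ=.6).

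| Ideation, 85 completers | Residual scale | Total scale | SAP |
|---|---|---|---|
| ρ=0 | 2,040 | 5,667 | 130 |
| ρ=.2 | 1,473 | 4,093 | 130 |
| ρ=.6 | 794 | 2,205 | 130 |

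Lab outcomes with ICC .50: 85×3.75 = 319 (residual) or 319/.50 = 638 (total), against 134.

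**Detectable contrast.** δ = (2.652+.842)×√[(τ²+v)/85], in units of σ, where v is .667 at ρ=0 and 1.714 at ρ=.6. The values of τ are assumed.

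| | τ=0 | τ=.5 | τ=1 |
|---|---|---|---|
| ρ=0 | .31 | .36 | .49 |
| ρ=.6 | .50 | .53 | .62 |

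**When could a low-ICC row be optimistic?** If the varying effect takes a share s of within-person variance, residual-scale effective N is 85/[s+(1−s)/24]. This is 364 at s=.2 and 163 at s=.5. Agitation (ICC .26, stated 292) then has 364/.74 = 492 down to 163/.74 = 221 on the total scale, so at s=.5 it falls below the stated figure on both scales. Power at f²=.10 is still at least .90. These shares mean τ = 4√[s/(1−s)], or 2 to 4 residual SD, which is more variation than in the table above. At τ=1 and ρ=.6, effective N is 16×85/2.714 = 501, above 292.

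**The case against.** The best defence is that nothing is lost. The tables follow consistently from the chosen formula, and for ideation and the ICC-.50 lab outcomes the formula understates power. At f²=.10 the claim of at least 80% power survives for the continuous outcomes in every scenario tried, and no one would enrol a different number. The SAP also leaves the hierarchical structure to model fit. It reports that nesting by condition did not improve fit in the prior trial, which is the only evidence bearing on how far effects differ between persons. All of this stands, except that the nesting result concerns person-by-condition variation, not variation in the condition-by-phase effect.

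Two qualifications also stand. The SAP never defines the denominator of f². Its wording points to total variance, but on the residual scale the ICC is irrelevant and no longer helps. And the largest discrepancy, about 44-fold for ideation (5,667/130), needs both total-variance scaling and zero autocorrelation. On the residual scale with ρ=.6 it is about 6-fold (794/130).

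What the defence does not rescue is the quoted rule about the ICC, which holds on neither scale, or the use of these tables as the stated basis for the sample size.

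**Conclusion.** The concern holds as a fault of method, not of arithmetic. The design effect does not apply to this contrast, so the stated effective Ns, powers and required Ns do not describe the trial. For ideation, effective N is about 790 to 5,670 instead of 130, depending on the f² scale and an assumed ρ of 0 to .6. With assumed τ of 0 to 1 within-person SD, 85 completers can detect about .31 to .62 within-person SD. The f²=.10 target is 1.26 on the residual scale, or 2.11 on the total scale at ICC .64.

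A reader might infer three stronger things that the documents do not support.

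- That the trial is too small. The error is conservative for ideation and the ICC-.50 lab outcomes, so it does not show that 85 or 90 completers are too few. Low-ICC rows are not guaranteed conservative, but only large person-to-person variation would make them optimistic.
- That the ranking of outcomes is simply reversed, with ideation the best powered. That needs f² on the total-variance scale.
- That the same linear correction gives valid power for the binary outcomes. Suicide attempt occurred on about 1.2% of days in the prior trial, or about 24 positive days in 2,040. Neither the SAP's table nor this calculation serves that outcome or suicidal planning.

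**What to change.** Replace the design-effect step with the variance of the within-person contrast, or with a simulation from the planned model. Take the residual variance, the AR(1) correlation and any condition-by-phase slope variance from the prior trial's data. State whether f² refers to total or residual variance. Restate power, or the detectable effect in within-person SD, for each continuous outcome at the protocol's target of 90 completers. At 90 the detectable contrasts above shrink by √(85/90) = .97. Use a simulation for suicidal planning and suicide attempt. Delete the sentence on the direction of the ICC, and bring the power paragraph in protocol section 10.0, which still refers to 80 completers, into line.

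The cost is one recalculation and a revision of the SAP and protocol text. Design and enrolment do not change.

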- b. For laboratory visit outcomes, we will again utilize multilevel models (with 6 labs per person—3 per condition—nested within individuals; two-level models). A two-level model will predict each repeated measures lab outcome from covariates (daily pain, illness, PRN medication use) and the interaction between (1) experimental condition (a dichotomous variable coded as 0 for natural hormone withdrawal condition and 1 for hormone stabilization condition) and (2) condition phase, a categorical (contrast) variable coded as follows: *midluteal baseline visit, perimenstrual experimental visit*, and the *medication withdrawal visit*. Number of lab observations per person. For the primary contrast between the midluteal and perimenstrual experimental phases, there are 4 observations per person—2 per condition. Based on our preliminary data from the K99 trial (identical experimental manipulation), we anticipate very minimal missing laboratory data (see grant for details) but have estimated that on average each completer participant will miss .25 visits.
- c. **Hypothesized Pattern of Effects for Daily and Lab outcomes**: A significant interaction between experimental condition and condition phase is hypothesized for all twelve specified outcomes such that, in the natural withdrawal condition we expect deleterious changes from the midluteal phase to the premenstrual and menstrual phases (due to corresponding hormone withdrawal), but in the hormone stabilization condition we expect no deleterious

1 R01 MH120843-01 (PI: [name])

changes (or less severe changes) from the midluteal to the premenstrual and menstrual phases (since hormone withdrawal is prevented).

2. Testing Associations Between Mediators and Suicide Outcomes: Each aim next requires that we evaluate the day-to-day or week-to-week associations between single mediators (listed above) and suicide outcome variables on the same day or visit. This will be carried out in similar multilevel models as above, predicting each of the three primary suicide outcomes from person-centered values for each of the 9 mediators (listed above).

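### The SAP's suicide-attempt power (.99 at 85 completers; 21 needed) rests on an effect size that attempts on about 1.2% of days cannot reach; a few other power entries need small corrections.

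*SAP*

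**What the plan says.** The SAP's Outcome Specification makes daily suicide attempt (aborted, interrupted or full; yes/no) one of three primary suicide outcomes, and reports that about "1.2% of days were positive for suicide attempt in the K99 trial; ICC=.12 in K99 trial".

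The SAP's Power Analysis defines the target f² = .10 as the interaction of condition and phase having "uniquely accounted for 10% of the variance in the outcome in the perimenstrual window". It tests one coefficient among three predictors, one-sided, at alpha .004. Effective N comes from a design-effect formula, "including 15% missing at daily level and an average of .25 missing visits per person". With that effective N in hand, the SAP says, "one can calculate power to detect a given effect size (in our case, f² = .10) for a given number of these" effective observations or visits.

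Two tables follow. The first gives power at 85 completers; for attempts, effective N is 542 and power .99. The supplemental table gives participants needed for 80% power; for attempts, 21. Its footnote begins: "First, we calculated the number of observations required using a normal GLM framework (non-multilevel".

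For laboratory outcomes, the SAP describes models "with 6 labs per person—3 per condition", but says that for the primary midluteal-to-perimenstrual contrast "there are 4 observations per person—2 per condition".

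The protocol's Power Analysis (section 10.0) attaches 80% power to 80 completers. The SAP attaches it to 85, and protocol section 3.0 plans 90.

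**The concern.** The calculation gives the rarest outcome the largest effective N (542) and the smallest participant requirement (21) of all twelve. This happens because its low ICC shrinks the design effect while the effect size stays at .10. A linear-model f² is a share of variance, and a binary outcome that is almost always zero has little variance between cells for an interaction to explain. If .10 is unreachable, the row says nothing about the trial's ability to detect an effect on attempts. A reader who trusted .99 would overstate what a non-significant attempt result can exclude, on the most serious of the primary outcomes.

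The same tables contain entries that disagree with each other. HRV has the same ICC, interval and number of participants as PEP in the first table, but a different effective N and power.

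**Working it through.** **1. Reproducing the SAP's method.** Inputs: n = 85; daily observations m = 28 × .85 = 23.8; laboratory observations m = 4 − .25 = 3.75; ICCs from the SAP's tables.

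- Effective N = n·m / (1 + (m − 1)·ICC).
- Power is from a noncentral t with noncentrality √(f²·N) and N − 4 degrees of freedom, one-sided alpha .004. For f² = .10, 80% power needs 126 observations.
- Participants needed = 126·(1 + (m − 1)·ICC)/m.

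Ideation: 2023/15.592 = 129.7, power .82, participants 82.5 (stated 130, .81, 83). Attempt: 2023/3.736 = 541.5, power above .99, participants 19.8 (stated 542, .99, 21). The method is therefore recovered, and the attempt arithmetic is sound given f² = .10. The fault lies in the effect size.

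**2. Ceiling on f² for attempts.** Take the SAP's four equal cells (two conditions by two 7-day phases) with mean daily rate p. The interaction is largest when all events fall in one cell, at rate 4p. Total variance is p(1 − p). The interaction explains p², and with both main effects the model explains 3p². Hence

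f² = p² / [p(1 − p) − 3p²] = p/(1 − 4p).

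At p = .012 this is .012/.952 = **.0126**, about one eighth of .10. Reaching .10 this way needs p = .10/1.4 = 7.1% of days.

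**3. The most favourable case.** Suppose 1.2% is the rate over all 52 days and every attempt falls in the placebo perimenstrual cell. That cell's rate is q = .012 × 52/7 = .089.

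- Four cells: mean .0223, f² = .024.
- Perimenstrual cells only: q/[2(1 − q)] = .049.
- Divided by the within-person share, 1 − .12 = .88: **.056**.

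As a share of variance, .056/1.056 = 5.3%.

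**4. Power at those ceilings, by the SAP's own method**

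| f² | 85 participants | 21 participants |
|---|---|---|
| .0126 | .48 | .09 |
| .024 | .83 | .19 |
| .049 | .993 | .45 |
| .056 | .998 | .52 |

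At f² = .0126, 80% power needs about 972 effective observations, or 972 × 3.736/23.8 ≈ 153 participants.

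**5. Simulation under assumed rates.** The documents give no rate ratio, so a range was assumed: placebo perimenstrual rate 2, 5 or 10 times the other cells; mean 1.2%; 85 people; 7 days per cell; 85% response; observed ICC between .12 and 0.

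- Person-level contrast test: power .02–.04, .28–.40 and .60–.80.
- Logistic interaction test: .03–.04, .16–.20 and .22–.27.
- All attempts in the one cell: .95–1.00 with the person-contrast test; the logistic interaction is then not estimable.
- With 21 people (person-contrast test): at most .06 for 2- to 10-fold rates, .02–.23 with all attempts in one cell, and at most .77 in the 52-day extreme of step 3.

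**6. Other entries**

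- HRV, first table: 318.75/2.375 = 134.2, power .83, as for PEP. The stated 163/.90 matches the daily count: 2023/12.4 = 163.1, power .91.
- Planning, supplemental table: 126 × 11.26/23.8 = 59.6, so 60, not 57 (57 gives power .78). The first-table entry reproduces (179.7 against 180).
- Laboratory rows, supplemental table: at 5.75 visits (6 less .25) the formula gives 74.0 and 52.1, matching the stated 74 and, rounded up, 53. At 3.75 visits, the first table's basis, it gives 79.8 and 60.4, so 80 and 61.
- Ideation power by completers: 80 gives .785, 83 gives .80, 85 gives .82, 90 gives .84.

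**The case against.** Several stronger readings are tempting, and the documents do not support them.

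- *That .99 is wrong in every case.* It is not. At f² of .049 to .056 the SAP's method gives .993 to .998, and simulation with all attempts in the placebo perimenstrual cell gives .95–1.00. The lower figures depend on assumed 2- to 10-fold rate ratios that the documents do not supply. What stands is that .99 was derived from an unreachable effect size and holds only near that extreme.
- *That f² = .10 is impossible on any scale.* On a latent logit scale it is reachable, at about a 10-fold ratio of odds ratios: exp(√(16 × .10 × 3.29)) = 9.9. But the SAP defines f² on outcome variance and uses a normal linear model.
- *That the SAP would abandon attempts as an outcome below 10% of variance.* The SAP says that if hormone withdrawal "does not account for at least 10% of the variance in the outcome during this critical risky window of the menstrual cycle", the line of research is not worth pursuing. That is a general rationale, not a decision rule for each outcome. It remains true that attempts cannot meet the benchmark at the stated rate.
- *That the supplemental laboratory figures are miscalculated.* They reproduce at 5.75 visits. The fault is an unstated change of basis between the two tables.
- *That the 1.2% input is wrong.* Over 52 days in 30 people it implies about 19 attempt-days (30 × 52 × .012 = 18.7), or 13 over 36 days. Protocol section 2.0 lists aborted attempts in 2 participants against 0, and section 4.1 says nobody attempted suicide. But one source counts days and the other people, one person can contribute several days, and interrupted attempts are not listed. A reader cannot settle it.

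It is also fair to say that the table corrections and the completer mismatch change no decision. Every corrected non-attempt requirement is below 85, and the protocol plans 90.

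**Conclusion.** The attempt rows are wrong as written. On the SAP's own scale the interaction f² is at most .0126 when 1.2% is the mean of the four 7-day cells, and at most about .056 in the extreme 52-day case, against the .10 used. The figure 21 is too few in every case examined. The figure .99 is not supported in general. This rests on the SAP's 1.2% day rate, its outcome-variance definition of f² and equal cells; the simulated powers rest also on the assumed rate ratios.

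The HRV entry, the supplemental planning entry and the mixed visit basis are minor table faults. The protocol's statement of 80% power at 80 completers is slightly too high for ideation (.785). None of this alters the sample size: ideation needs 83, that row reproduces, and 90 are planned.

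**What to change.** - Remove 21 and replace the attempt row in both tables with power simulated from a logistic mixed model at the stated day rate, over a stated range of rate ratios.
- Base that simulation on days with a scheduled phone screen. Protocol section 6.0 places the calls on medication days and the 4 days after, with medication starting on day +7, so only one day of the +1 to +7 baseline phase is covered. State how cells with no attempts are handled: in the 10-fold simulation a cell was empty in 39–44% of runs with 7 days per cell, and in about 95% with one baseline day.
- Say that the 10%-of-variance benchmark is not attainable for attempts at this rate.
- Confirm the 1.2% input against the prior trial's data.
- Correct HRV in the first table to 134/.83, or replace the HRV and PEP rows if the Oura Ring has superseded those laboratory measures (protocol section 6.0).
- Correct planning in the supplemental table to 60. Put both tables on one visit basis; at 3.75 visits the laboratory entries become 80 and 61.
- Align the completer count in protocol section 10.0 with the SAP's 85 and the planned 90.

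The cost is a short simulation and wording changes in the SAP and protocol. No extra participants are needed.
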